#### Serious Adverse Event (SAE)

A SAE is an AE that results in one of the following outcomes or constitutes one of the following events:

- Death;
- Initial or prolonged inpatient hospitalization (other than that required by protocol; “social hospitalization” or any hospitalization for non-medical reasons does not constitute a SAE);
- A life-threatening experience (that is, immediate risk of dying);
- Persistent or significant disability/incapacity;
- Congenital anomaly/birth defect;
- Considered significant by the investigator for any other reason.

Important medical events that may not result in death, be life-threatening, or require hospitalization may be considered serious adverse drug events when, based upon appropriate medical judgment, they may jeopardize the patient and may require medical or surgical intervention to prevent one of the outcomes listed in this definition.

#### Unexpected Adverse Event

An unexpected adverse event is an adverse event not previously reported or an adverse event that occurs with specificity, severity or frequency that is not consistent with the current IB.

#### Relationship to Study Drug

Investigators will be instructed to report their assessment of the potential relatedness of each adverse event to protocol procedure or study drug. The assessment of the relationship of an adverse event to the administration of the study drug is a clinical decision based on all available information at the time of the completion of the eCRF.

#### Intensity/Severity of an Adverse Event

In addition to assessing the relationship of the administration of the study drug to adverse events, an assessment is required, in order to determine the intensity (severity) of the event.

The following classifications should be used:

*Mild:*

A mild adverse event is an adverse event, usually transient in nature and generally not interfering with normal activities.

*Moderate:*

A moderate adverse event is an adverse event that is sufficiently discomforting to interfere with normal activities.

*Severe:*

A severe adverse event is an adverse event that incapacitates the subject and prevents normal activities. Note that a severe event is not necessarily a serious event; nor must a serious event necessarily be severe.

**7.7.3 Adverse Event Documentation**

All adverse events must be fully recorded on the adverse event eCRFs. Documentation must be supported by an entry in the subject file. Laboratory tests, vital signs and ECG abnormalities considered by the Investigator to be clinically relevant should be reported on the adverse event eCRFs. Signs and symptoms of each AE should be described in detail (e.g., start and stop dates, severity/intensity, relationship to study drug, action taken, and event resolution).

Adverse events and laboratory test abnormalities fulfilling the definition of a serious adverse event should, in addition, be reported on the Serious Adverse Event Reporting Form.

**7.7.4 Reporting of Serious Adverse Events**

Study site personnel must alert Eli Lilly, or its designee, of any SAE within 24 hours of their awareness of the event via a sponsor-approved method. Alerts issued via telephone are to be immediately followed with official notification on study-specific SAE forms.

Serious adverse events occurring after a subject receives a dose of study drug will be collected until 48 hours after the dosing of the study drug, regardless of the investigator's opinion of causation. Therefore, SAEs that occur later than 48 hours after the dosing of the study drug are not required to be reported unless the investigator feels the events were related to either study drug or a protocol procedure.

If a patient experiences a SAE after signing informed consent, but prior to receiving study drug, the event will NOT be reported unless the investigator feels the event may have been caused by a protocol procedure. Previously planned (prior to signing the ICF) surgeries should not be reported as SAEs unless the underlying medical condition has worsened during the course of the study.

## 8. STATISTICAL ANALYSIS

### 8.1 General Statistical Considerations

All statistical analyses will be performed using SAS® version 8.2 or higher.

The study data collected under the BIOCARD protocol, such as but not limited to subjects' demographic and baseline characteristics, medical history, neurological and behavioral evaluations, neuropsychological test results, MRI, and other biomarker studies will be transferred to Avid for analysis purposes.

Additional details concerning statistical analyses will be included in the Statistical Analysis Plan (SAP) to be completed per Avid SOP.

### 8.2 Safety Analysis

Adverse events including injection site reactions will be summarized in terms of number and percentage of subjects experiencing an AE. The summary will be further broken down by system organ class (SOC) and preferred term using Medical Dictionary for Regulatory Activities (MedDRA) terms. Adverse events will also be presented by severity, relationship to treatment and seriousness. All subjects who experience SAEs, or who discontinue due to AEs, will be summarized.

#### Discontinuation

All subjects who discontinued participation prior to completing the study will be listed and their discontinuation reasons will be tabulated.

### 8.3 Image Analysis

All flortaucipir (F) PET images obtained starting at 75 minutes post injection will be analyzed. Additional details concerning image analyses will be included in a separate document to be completed prior to the end of the study.

### 8.4 Exploratory Analyses

Exploratory analyses will examine the relationship among flortaucipir (F) uptake measurements, cognitive and neuropsychiatric measurements, and other collected biomarkers in subjects, and will explore whether the flortaucipir (F) uptake measurements are correlated with other biomarkers, cognitive status, and clinical presentation. Additional retrospective analyses will be conducted to explore the possible risk factors of tau deposition.

## 9. USE OF DATA AND PUBLICATION

Avid adheres to the Pharmaceutical Research and Manufacturers of America (PhRMA) Principles on Conduct of Clinical Trials and Communication of Clinical Trial Results. A complete copy of these principles is available from Avid and can also be found at the PhRMA website (<http://www.phrma.org>). Avid's policy is briefly summarized below:

- We commit to timely communication of meaningful results of controlled clinical trials, regardless of outcome.
- As a sponsor, we may recommend that the Investigator(s) delay or decline publication in cases where the study design, conduct, or data are insufficient to allow meaningful interpretation. Avid and the Investigator(s) will discuss the study design and data in advance of the study, and again after completion, and will strive, through appropriate scientific debate, to reach a consensus regarding the potential merits of publication.
- Avid retains the right to review any manuscripts, presentations, or abstracts before they are submitted for publication. Where differences of opinion or interpretation exist regarding data planned for publication, the parties (Avid and the Investigator) should try to resolve them through appropriate scientific debate. Avid retains the right to delay publication for up to 60 days to protect intellectual property.
- Anyone who provides substantial contributions should receive appropriate recognition as an author or contributor when the manuscript is published.

## 10. INVESTIGATOR'S REGULATORY OBLIGATIONS

All clinical work conducted under this protocol is subject to Good Clinical Practice regulations; this may include an inspection by Avid and/or Health Authority representatives (FDA or international regulatory authorities) at any time.

### 10.1 Institutional Review Board (IRB)

The intent of the research program, the trial protocol, the patient information/informed consent form and any advertising material used to recruit subjects must be submitted to the clinical investigator's local IRB and its approval must be obtained prior to its use. A copy of the approval must be forwarded to Avid. When necessary, an extension or renewal of IRB approval must be obtained and also forwarded to Avid.

### 10.2 Informed Consent

A signed, written informed consent must be obtained from each patient. A copy of the signed informed consent should be given to the patient for their records. A copy of the local IRB's approved version of the informed consent form must be forwarded to Avid, or its designee, for review prior to being used to obtain patient consent.

### 10.3 Protocol Adherence

The protocol must be read thoroughly and the instructions must be followed exactly. Where a deviation occurs, it must be documented, the sponsor/monitor informed, and a course of action agreed upon.

### 10.4 Documents Necessary for Initiation of the Trial

Avid must be provided with the following documents prior to the enrollment of any subjects:

- Original signed and dated Statement of Agreement page;
- Copy of the IRB and radiation safety committee approval (if applicable);
- Copy of the IRB stamped approved consent form;
- Name and location of the laboratory utilized for laboratory assays, and other facilities conducting tests, including laboratory certification number and date of certification if available;
- List of reference range laboratory values; and
- Any additional licenses required in order to order to use flortaucipir ( $^{18}\text{F}$ ).

### 10.5 Study Drug Control

The receipt of clinical supplies (e.g. starting material for flortaucipir ( $^{18}\text{F}$ )) must be documented at the site.

All drug supplies for this trial should be retained in a safe and secure place at all times during the trial. Flortaucipir ( $^{18}\text{F}$ ) should be prepared by a qualified PET manufacturing site and administered by a qualified individual under the investigator's supervision. An up-to-date drug inventory/dispensing record must be maintained and all drug supplies must be justified. After completion of the trial, all remaining clinical supplies must be returned to the sponsor, or their representative.

### 10.6 Data Collection

Electronic case report forms (eCRFs) will be used for this trial. Individual patient files should include appropriate source documents, including but not limited to patient's medical records and laboratory test results. The files should include information such as visit dates, records of medical history, examinations administered, laboratory, concomitant treatment, any adverse event encountered and other notes as appropriate. These constitute "source data". All entries on the eCRFs must be backed up by source data. Original electronic versions of imaging studies are also considered source data and should be kept on file by the site/imaging center, and appropriate copies should be forwarded to Avid as specified in the imaging manual.

Each patient's source file should include an original signed informed consent form. When the trial is completed, the informed consent form should be kept on file with other trial related records.

All original laboratory reports must be available for review in each patient's file. It is important that the original reports be available for review because of the possibility of inaccuracies or errors in transcribing data from original records to the eCRF.

The eCRFs must be kept in order and up-to-date so that they always reflect the latest observations on the subjects that are enrolled in the trial. The eCRFs must be completed for each patient enrolled in the trial and signed by the investigator. This should be done as soon as possible after completion of the patient's participation in the trial. A monitor will verify the source data for all information on the eCRF.

### **10.7 Adverse Events**

All adverse events encountered during the clinical trial must be documented on the eCRF, whether or not considered drug-related.

Eli Lilly must be notified immediately (as soon as possible, and in all cases within 24 hours) of a drug experience, condition, development, or event, which is considered serious. Eli Lilly must be notified immediately of any findings with the use of the drug that may suggest significant hazards, contraindications, adverse drug reactions (ADRs) and precautions pertinent to the safety of the drug. The investigator will be requested to complete a separate report form in addition to the information on the eCRF. See section 7.7.4 for reporting serious adverse events

If a SAE is determined to be unexpected (not previously reported or described by Avid), and study drug-related, Eli Lilly will notify the investigator in writing. The investigator should forward this notification to the IRB within 24 hours of receipt.

### **10.8 Records Retention**

All correspondence (e.g., with Avid, IRB, etc.) relating to this clinical trial should be kept in appropriate file folders. Records of subjects, source documents, and drug inventory sheets pertaining to the trial must be kept on file. Records must be retained until the date a marketing application (NDA) is approved for the drug for the indication for which it is being investigated, or until 2 years following the date of clinical trial termination or completion, whichever is later. If no application is to be filed, or if the application is not approved for such indication, records should be kept until 2 years following the date of clinical trial termination or completion.

If an investigator moves, withdraws from an investigation, or retires, the responsibility for maintaining the records may be transferred to another person who will accept the responsibility. Notice of transfer must be made to and agreed upon by Avid.

### 11.2 Trial Flow Chart

Evaluations	Screening Assessments a	 F-AV- 1451 Imaging Visit	End of  F-AV- 1451 Imaging (prior to discharge)	Follow-up Phone Call b
Signed Informed Consent	X			
Demographics	X			
Medical History	X			
Concomitant Medications	X			
ECG	X c			
PET Brain Scan		X d, e		
Evaluation by a physician	X	X f	X g	
Pregnancy Test	X h	X i		
Adverse Events	X	X	X	X
Serious Adverse Events	X	X	X	X

- a. Screening may take place over several days. All assessments must be performed within 90 days prior to the flortaucipir (F) imaging session. Subjects may be permitted to return for the flortaucipir (F) PET scan after the 90 day window with sponsor approval if the investigator does not recognize any significant medical changes.
- b. A follow-up phone call to the subject, or information where applicable, will be conducted within 2 or 3 business days of each imaging day, but not before 48 hours post-injection, to confirm subject well-being and to collect information about any new adverse events. If both of these days are not business days, the follow-up phone call can occur the following business day.
- c. ECG (with results reviewed prior to flortaucipir (F) administration).
- d. Subjects will receive a single IV bolus injection target dose of 370 MBq (10 mCi) of flortaucipir (F) injection followed by a saline flush.
- e. At approximately 75 minutes following flortaucipir (F) injection, a continuous 30-minute brain scan will begin.
- f. Or a licensed/credentialed medical professional (i.e. PET technologist, imaging center nurse or a regional equivalent) designated by the site principal investigator. If a designee performs this activity, the physician must be available to provide medical consultation.
- g. Or physician designee.
- h. Serum pregnancy test
- i. Urine pregnancy test prior to flortaucipir (F) injection

1 LIST OF ABBREVIATIONS AND DEFINITIONS OF TERMS

Table 1: Abbreviations and Definitions of Terms

AAL	Automated anatomical labeling
A β	amyloid- β
AD	Alzheimer's disease
AE	adverse event
BIOCARD	Biomarkers of Cognitive Decline Among Normal Individuals
CRF	Case report form
CSF	cerebrospinal fluid
CSR	clinical study report
ECG	electrocardiogram
IV	intravenous
MBq	megabecquerel
mCi	millicuries
MedDRA	Medical Dictionary for Regulatory Activities
MMSE	Mini-Mental State Examination
MUBADA	Multiblock Barycentric Discriminant Analysis
PERSI	parametric estimated signal reference intensity
PET	positron emission tomography
PiB	Pittsburgh compound B
PT	preferred term
SAE	Serious adverse event
SAP	statistical analysis plan
SAS	Statistical analysis software
SOC	system organ class
SUV _r	standardized uptake value ratio
TEAE	treatment-emergent adverse event
WHO	World Health Organization

2 INTRODUCTION

Of the 2 pathological protein deposits that are the hallmark of Alzheimer's disease (AD), beta- amyloid (A β) is thought to accumulate very early in the disease process and is frequently observed in elderly subjects with no clinical symptoms, a condition that may represent a preclinical phase of the disease. Furthermore, as a biomarker, A β plaques as seen on PET amyloid imaging appear to plateau in intensity early in the symptomatic phase of the disease.

In contrast to A β deposits, the density and distribution in the brain of phosphorylated tau, in the form of neocortical tangle pathology, has been shown in autopsy studies to be increased with AD-related cognitive impairment and appears to correlate with overall evidence of neurodegeneration across the entire spectrum of the illness (Duyckaerts et al. 1987; Nelson et al. 2012). Thus, an understanding of the onset and progression of tau pathology in relation to amyloid pathology and cognitive change may be critical to understanding the course of the disease.

It is important to evaluate cognitive normal subjects with elevated brain amyloid to obtain information regarding the presence/onset of tau pathology because clinically normal amyloid positive subjects have been hypothesized to represent the earliest preclinical stage of AD (Sperling et al., 2011). The present study planned to obtain flortaucipir (¹⁸F) tau positron emission tomography (PET) scans in up to 100 clinically normal subjects from the Biomarkers of Cognitive Decline Among Normal Individuals (BIOCARD) study that have been identified as having elevated brain amyloid by PET or cerebrospinal fluid (CSF) assays.

3 STUDY OBJECTIVES

The primary objectives of this study are:

- To evaluate imaging characteristics of flortaucipir (¹⁸F) with respect to brain amyloid status in subjects who are enrolled in the BIOCARD study
- To examine the relationship between cognitive and function performance, other biomarker data, and tau deposition as measured by flortaucipir (¹⁸F) uptake in clinically normal subjects

A secondary objective of this study is:

- To expand the flortaucipir safety database.

4 STUDY DESIGN

4.1 General Design

This is a phase I study that will evaluate imaging characteristics of flortaucipir in subjects enrolled in the BIOCARD study. Subjects enrolled in the BIOCARD study were contacted to participate and must have provided informed consent before starting any AV-1451-A20 study procedures. In addition to consenting to study procedures, participants consented to have Magnetic Resonance Imaging (MRI) images/data,

laboratory data, medical and neuropsychological assessments, as well as amyloid status, and lumbar puncture results made available to this study to allow for analysis and comparison. This study hoped to recruit roughly 80 percent amyloid positive subjects, and 20 percent amyloid negative subjects from the BIOCARD study. Amyloid positivity (Aβ+/Aβ-) was determined based on a visual read of the BIOCARD Pittsburgh compound B (PiB) amyloid PET scan. A list of subjects to be targeted for recruitment, including appropriate numbers of both amyloid positive and amyloid negative cases, was provided to the site. The subjects' amyloid status were not revealed to the site or subjects as part of recruitment or inclusion for this study.

Flortaucipir PET Imaging Session:

For the flortaucipir PET imaging session, an intravenous (IV) catheter was placed for administration of flortaucipir injection. Subjects received a single IV bolus injection target dose of 370 megabecquerel (MBq) (10 millicuries (mCi)) of flortaucipir injection followed by a saline flush. At approximately 80 minutes post dose, a continuous 20-minute brain scan (4 acquisitions of 5-minute duration) was obtained. If at any point during the imaging session it was determined that the subject was not able to continue, or that it was not in the best interest of the subject to continue, the protocol specified that imaging would be discontinued, and the image data that had been collected up to that point would be analyzed. Clinical laboratory tests were obtained prior to injection and upon completion of each imaging session. Adverse events (AE) were monitored continuously during the imaging session. Subjects who experienced any AE during an imaging session were not discharged until the event had resolved or stabilized.

4.2 Method of Assignment of Subjects to Treatment Groups

Subjects who qualify for the study will return to the clinic at a later date for the flortaucipir (¹⁸F) PET imaging visit. For the flortaucipir PET imaging visit, an intravenous catheter will be placed for IV administration of flortaucipir (¹⁸F) injection. Subjects will receive a single IV bolus injection with a target dose of 370 MBq (10 mCi) of flortaucipir (¹⁸F) injection followed by a saline flush.

4.3 Blinding

The study recruited roughly 80 percent Aβ+ subjects and 20 percent Aβ- subjects from the BIOCARD study. Amyloid positivity was determined by an Avid expert reader's visual interpretation. A list of subjects for recruitment was randomly selected, stratifying by amyloid status to maintain an approximately 80% Aβ+ subjects. The list was provided to the site with amyloid status blinded. The subjects' amyloid status were not revealed as a part of recruitment or inclusion for this study.

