A relatively small number of subjects in the ongoing A05 study presented cognitively as clinically normal with elevated brain amyloid. It is important to evaluate additional subjects of this type to obtain information regarding the presence/onset of tau pathology because clinically normal amyloid positive subjects have been hypothesized to represent the earliest preclinical stage of AD (Sperling et al., 2011). The present study will obtain flortaucipir ( $^{18}\text{F}$ ) tau PET scans in 100 clinically normal subjects from the BIOCARD study that have been identified as having elevated brain amyloid by PET or CSF assays.

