7.6 Examination of Subgroups

No subgroup analysis will be conducted for this study.

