8.4.1.3 Correlation between MMSE and MUBADA SUVr in Clinically Normal Subjects

Spearman's correlation coefficient will be used to measure the relationship between baseline MMSE and MUBADA SUVr in clinically normal subjects. This relationship will also be presented in a scatter plot.

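### The MMSE and FAQ correlations with tau uptake combine two amyloid strata sampled at a designed ratio of about 80/20, with no amyloid-adjusted or within-stratum estimate beside them (minor; cheap to improve)

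*SAP*

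**What the plan says.** **Sampling.** SAP 4.1 states the target: "This study hoped to recruit roughly 80 percent amyloid positive subjects, and 20 percent amyloid negative subjects from the BIOCARD study". SAP 4.3 gives the mechanism: "A list of subjects for recruitment was randomly selected, stratifying by amyloid status to maintain" a share of about 80% positive. Protocol 5.1 has the same target. The amyloid mix is therefore set by design.

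**Objective.** The second primary objective (SAP 3) is "To examine the relationship between cognitive and function performance, other biomarker data, and tau deposition as measured by flortaucipir" uptake, in clinically normal subjects.

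**Analysis.** SAP 8.4.1.3: "Spearman's correlation coefficient will be used to measure the relationship between baseline MMSE and MUBADA SUVr in clinically normal subjects". SAP 8.4.1.4 applies the same method to FAQ. Neither section has an amyloid term, split or weight, and SAP 8.1.3 assigns efficacy endpoints to the whole efficacy population. SAP 6.4.2.1 and 6.4.2.2 tie both scores to the primary objective analysis.

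**Stratified results.** SAP 8.4.1.1 and 8.4.1.2 report the visual read and MUBADA SUVr by amyloid status. For everything else SAP 7.6 says: "No subgroup analysis will be conducted for this study".

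**Size.** SAP 4.4 reports 23 dosed subjects with a read or quantification, and no power calculation. The split achieved among the 23 is not given.

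**The concern.** Amyloid status is the design variable, and the first objective's results are reported by it, yet it drops out of the analyses for the second objective. Tau uptake may differ by amyloid status, and cognition may too. In that case a correlation over both groups combines two things: the difference between the groups, and the relation between tau and cognition within each group. The weight of each part depends on the share of positives, which the recruitment list fixed.

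Two misreadings become possible. A non-zero coefficient could appear with no relation inside either group. Or a relation confined to positives could be weakened, or left unchanged, by including the negatives. The planned output cannot tell a reader which of these applies. These two coefficients are the only planned analyses of the cognitive and functional part of a primary objective.

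**Working it through.** The documents state no effect size, power or expected coefficient, so there is no plan figure to reproduce. All stratum parameters below are assumptions, with normal data. Scores that bunch at the top of MMSE or the bottom of FAQ are not modelled. For FAQ, where higher is worse, the signs reverse.

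**Inputs.** Share positive p = 0.8 (SAP 4.1, 4.3); n = 23 (SAP 4.4); 0.8 × 23 = 18.4, so about 18 positive and 5 negative if the target was met; two-sided 0.05 (SAP 7.1).

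**Step 1: pooled coefficient with zero correlation inside both groups.** Let positives be shifted by d_s SD on SUVr and d_c SD on cognition. On the Pearson scale,

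r = p(1-p)·d_s·d_c / √{[1 + p(1-p)·d_s²]·[1 + p(1-p)·d_c²]}, with p(1-p) = 0.16.

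- d_s = 1, d_c = -0.5: -0.08 / √(1.16 × 1.04) = -0.07.
- d_s = 1.5, d_c = -1: -0.24 / √(1.36 × 1.16) = -0.19.

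Large-sample simulation on the Spearman scale (400,000 draws) gives -0.07 and -0.18.

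**Step 2: when the mix matters.** Pooled Spearman coefficient from the same simulation:

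| Assumed scenario | 50% positive | 80% positive | Positives only |
|---|---|---|---|
| No within-group correlation; shifts +1, -0.5 SD | -0.11 | -0.07 | 0.00 |
| No within-group correlation; shifts +1.5, -1 SD | -0.28 | -0.18 | 0.00 |
| Correlation -0.3 in positives only; no shifts | -0.15 | -0.23 | -0.29 |
| Correlation -0.3 in positives only; shifts +1, -0.5 SD | -0.23 | -0.29 | -0.29 |
| Same joint distribution in both groups, correlation -0.3 | -0.29 | -0.29 | -0.29 |
| SUVr shift only, no within-group correlation | 0.00 | 0.00 | 0.00 |

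The last two rows show no dependence on the mix. In the fourth row the pooled value at 80/20 happens to equal the value in positives.

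**Step 3: a test at the actual size.** With 18 + 5 subjects, zero correlation in both groups and a nominal 5% test, 100,000 simulated trials reject in 6.3% (+1, -0.5 SD) and 13.6% (+1.5, -1 SD). The sampling SD of the coefficient is about 0.2 in both cases. A partial Spearman coefficient adjusted for amyloid status rejects in about 5% of trials in both. SAP 8.4.1.3 does not itself call for a p-value, so the rejection rate matters only if one is reported under the SAP 7.1 default.

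**Step 4: precision.** 95% half-width around zero by Fisher's z, tanh(1.96/√(n-3)):

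- All 23: tanh(1.96/√20) = 0.41.
- Partial, one covariate: tanh(1.96/√19) = 0.42.
- 18 positives: tanh(1.96/√15) = 0.47.
- 5 negatives: tanh(1.96/√2) = 0.88.

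**The case against.** The best defence is that a marginal correlation is a legitimate summary in an unpowered exploratory study. The enrichment is openly stated, and SAP 8.1.2 lists every efficacy variable by subject, so amyloid status can be matched to the scores. The documents place amyloid early in the disease process, so whether to condition on it is a choice. The dependence on the mix is conditional, and at n = 23 random error exceeds each of the shifts from zero in Step 1. SAP 7.6 bars subgroups but does not clearly bar an adjusted coefficient. All of this stands, and it is why the point is minor. It does not remove the ambiguity: a larger sample would not cure it, and per-subject listings are not an estimate.

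Three stronger readings are tempting, and the documents do not support them.

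- A reader might infer that the recruitment ratio alone can change the answer almost threefold. That needs a correlation of -0.5 in positives, exactly 0 in negatives, equal means, and a comparison of 80% with 30% positive (0.8/0.3 = 2.7). The 30% share appears nowhere in the documents, and equal means contradicts the worry that the groups differ. With the shifts assumed above, the values are -0.43 against -0.21 (factor 2.1) and -0.52 against -0.32 (factor 1.6).
- A reader might infer that the second objective targets BIOCARD subjects in their natural mix. It names only clinically normal subjects; BIOCARD is named in the first objective. No document gives the natural mix or makes it the target.
- A reader might infer that the study exists to estimate the tau-cognition relation within positives. Protocol 1 says "clinically normal amyloid positive subjects have been hypothesized to represent the earliest preclinical stage of AD", but offers this as a reason to study the presence and onset of tau. The by-amyloid summaries in SAP 8.4.1.1 and 8.4.1.2 address that.

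**Conclusion.** The point holds in a limited form. The pooled MMSE and FAQ coefficients can mix a between-group difference with the within-group relation, in proportions set by the sampling design, and the plan offers nothing beside them to separate the two. This happens only if the groups differ in both uptake and cognition or in their within-group correlation. The documents neither establish nor exclude that.

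Under the assumed shifts the pooled coefficient is about -0.07 to -0.18 when the within-group relation is nil, with 6% to 14% rejection at a nominal 5%. The real size and direction cannot be derived from the documents, and the 18/5 split assumes that the target was met.

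The introductions (Protocol 1, SAP 2) describe all subjects as having elevated amyloid. If that were so the issue would vanish, but it conflicts with the 80/20 design and should be reconciled. Rating: minor, a cheap improvement; the plan contains no error on this point.

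**What to change.** In SAP 8.4.1.3 and 8.4.1.4:

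- Keep the pooled Spearman coefficient and label it as applying to the amyloid-enriched sample.
- Add a partial Spearman coefficient adjusted for amyloid status as defined in SAP 6.4.1.3, with a 95% confidence interval. It removes the between-group shift, but it still averages over the groups if their correlations differ.
- For that reason, add the coefficient in amyloid-positive subjects, also with a 95% confidence interval.
- Mark amyloid status on the planned scatter plots.

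Amend SAP 7.6 to allow these analyses.

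The cost is SAP wording and a few lines of code; amyloid status was already needed to build the recruitment list. The interval in positives is somewhat wider (about ±0.47 against ±0.41 around zero), and the adjusted coefficient costs almost nothing (±0.42). The roughly 5 negatives give no useful estimate of their own (±0.88), so none should be presented as informative.
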